# 6.4.2. Secondary Efficacy Analyses

The Duration of Response (DOR) is defined as the time between the date of first response and the subsequent date of objectively documented progression of disease or death. The CR or PR will be derived based on investigators or independent radiologist assessment. The censoring rule is shown in Table 6.

Overall survival (OS) is defined as the time between the first dosing date and the date of death. Progression free survival (PFS) is defined as the time from the first dosing date to the date of the first documented progression or death due to any cause, whichever occurs first. The censoring rule is illustrated in Table 6 and Table 7.

Duration of response (DOR), PFS, and OS will be analyzed using Kaplan-Meier product-limit estimates. Median PFS and OS will be presented with 2-sided 95% CI if estimable. Censoring rules (Table 6, Table 7) is based on the Food and Drug Administration Guidance for Industry

Clinical Trial Endpoints for the Approval of Cancer Drugs and Biologics (2007). The cumulative PFS and OS will be plotted over time.

The Disease Control Rate (DCR) is defined as the proportion of patient with objective evidence of CR, PR, or SD, except that there is no requirement for a confirmation of an SD response. DCR will be calculated and a 2-sided Clopper–Pearson 95% CI will be constructed.

Table 6. Censoring Rules for Progression-Free Survival

No.	Situation	End Date	Outcome
1	Documented PD between scheduled visits a	Date of the first assessment of the series of the tests that determined PD	PFS event
2	Death during the study in absence of PD	Date of death	PFS event
3	Patients still on treatment without PD as of data cut-off b	Date of last tumor assessment c	Censored
4	Treatment discontinuation for other than PD or death, and no post baseline tumor assessments	Date of first dose	Censored
5	Treatment discontinuation for other than PD or death with post baseline tumor assessments	Date of last tumor assessment	Censored
6	New anticancer treatment started before PD or death	Date of last tumor assessment c before start of new treatment	Censored
7	Death or PD after two or more missed tumor assessments d	Date of the last tumor assessment c before missed assessments	Censored
8	No baseline or unreadable baseline assessment but readable post baseline assessments	Date of first dose	Censored

- a. If documented PD and/or death occurs after the last dose, it is counted as a PFS event as long as the PD and/or the death occurs within 21 days since the date of the last dose of study drug and provided that it does not violate other censoring rules (e.g. start of new anticancer therapy before the PD or death). Otherwise the patient will be censored on the date of last tumor assessment before the date of last dose date + 21 days.
- For PFS analysis, the date of last tumor assessment refers to the date of last adequate tumor assessment of CR, PR, SD, or PD.
- c. This refers to patients who were still receiving study treatment at time of data cutoff.
- d. Two or more missed tumor assessments is defined as having either one of the following two durations being longer than 2 cycles for the first 6 months of treatment, or thereafter 3:
  - Duration between two consecutive tumor assessments
  - Duration between the last tumor assessment and death or PD.

Table 7. Censoring Rules for Overall Survival (OS).

Situation	End Date	Outcome
Death before cut-off	Date of death	Death
Death after data cut-off	Date of data cut-off	Censored event
Patient still alive at data cut-off	Date of data cut-off	Censored event
Patient discontinued treatment due to	Date last known to be	Censored event
any reason before data cut-off	alive	

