PRO (EQ-5D and EORTC QLQ-C30)		X					X			Evaluated at screening and as close as possible to the tumor assessment schedule: at the end of every 2 cycles (up to +2 weeks) through Cycle 4 and every 3 cycles (± 7 days) thereafter until disease progression or initiation of new anticancer therapy (whichever is first).	
Tumor assessments / scans		X					X		(X)	
Same tumor assessments/scans obtained at screening at the end of every 2 cycles (up to +2 weeks) up to Cycle 4. Thereafter tumor assessments may be performed every 3 cycles (± 7 days), or as clinically indicated, until radiologic PD or initiation of new anticancer therapy (whichever occurs first).
 
At EOT, tumor assessment must be performed if the prior scan was performed ≥ 9 weeks prior to discontinuation of treatment if the patient discontinued for reasons other than radiologic disease progression. See also Section 9.17.
 
After EOT, patients who discontinued for reasons other than radiologic disease progression should continue to receive tumor assessments every 3 cycles (± 7 days), or as clinically indicated, until radiologic disease progression or initiation of new anticancer therapy (whichever occurs first).
	

	Pre-Screening	Screening Period (Within 28 Days Prior to First Dose)	Treatment Period (1 cycle = 21 days)				Safety Follow-up		Survival Follow-up Period	Notes
			Cycle 1			Cycles ≥ 2	End of Tx (+0-7 days)	30 (± 3) days After Last		
			Day 1	Day 4 ($\pm 1d$)	Day 8 ($\pm 3d$)	Day 15 ($\pm 3d$)				
Survival status								X	After discontinuation of treatment, survival follow-up should occur every 3 months (± 2 weeks) for up to 18 months after last patient enrolled in the Phase 2 portion of the study.	
TAS-120 Dosing			—————→							Patients are required to fast for ≥ 2 hours before and 1 hour after each administration of TAS-120; patients are permitted to drink water. TAS-120 should be administered in the morning or evening, at the same time (if possible) each day. See Section 8.1.1.

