9.17. Tumor Assessments/Scans

9.17.1. Tumor Assessment for Advanced Solid Tumors

Tumor assessments/imaging studies of the chest, abdomen, and pelvis (as clinically indicated) must be obtained at each time point listed below for all patients with solid tumors.

- Screening within 28 days prior to Day 1 of Cycle 1. Computed tomography scans obtained prior to the signed ICF may be used as the screening scan if they were obtained within 28 days of the first dose of TAS-120.
- At the end of every 2 cycles (up to +2 weeks), up to Cycle 4.
- Following Cycle 4, at least after every 3 cycles (\pm 7 days) or as clinically indicated, until documented progression (including after end of treatment if the patient discontinues for reasons other than radiologic disease progression).
- At end of treatment (+0-7 days), a CT scan must be performed if the prior scan was performed \geq 9 weeks prior to discontinuation of TAS-120 treatment if the patient discontinued for reasons other than radiologic disease progression.

On-site tumor assessments will be performed by the investigator/local radiologist according to RECIST guidelines (version 1.1, 2009). Results of these assessments, including response for target and non-target lesions and appearance of new lesions, will be the basis for the continuation or discontinuation of TAS-120. Response definitions are provided in [Section 10](#), Efficacy Assessment Criteria.

If the investigator determines that a patient has developed clinical progression manifested by symptomatic deterioration but not supported by radiologic evidence of progression, the patient should stop treatment. Symptoms of clinical progression must be documented in the patient's source documents and must be reported as AEs. Every effort should be made to document objective progression even after discontinuation of treatment.

The same method of assessment and the same technique must be used to characterize each identified and reported lesion at Screening, throughout the study, and during the follow-up period.

On-site tumor assessments will be conducted. Tumor assessment scans from patients with iCCA treated at 16, 20 and 24 mg QD and patients with primary brain tumors may also be prospectively or retrospectively collected and forwarded to the core imaging laboratory.

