12.2.2.3. Duration of Response

Duration of response (DOR) is derived for those patients with objective evidence of PR or CR. Duration of response is defined as the time from the first documentation of response (CR or PR) to the first documentation of objective tumor progression or death due to any cause, whichever occurs first. Patients who are alive and progression-free as of the analysis cut-off date will be censored at their last evaluable tumor response assessment prior to initiation of any new anticancer cancer treatment. Patients who start subsequent anticancer therapy without a prior reported progression will be censored at the last tumor assessments prior to initiation of the subsequent anticancer therapy. This endpoint will only be evaluated in patients with objective response of CR or PR.

Duration of response will be analyzed as a time-to-event endpoint with the median (Kaplan-Meier estimate) and associated 95% CI (Brookmeyer-Crowley methodology) reported.

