12.2.2.4. Progression-free Survival

Progression-free survival (PFS) is defined as the time from the day of the first dose to the date of first objectively documented disease progression or death (any cause), whichever occurs first. Patients who die without a reported disease progression will be considered to have progressed on the date of their death. Patients who did not progress or die will be censored on the date of their last tumor assessment. Patients who did not have any on-study assessments and did not die will be censored on the first dosing date. Patients who started any subsequent anti-cancer therapy without a prior reported progression will be censored at the last tumor assessment prior to initiation of the subsequent anti-cancer therapy. Early progression rate (EPR) for the GBM or Grade III glioma cohort will be assessed as the progression-free rate at the end of Cycle 2.

Progression-free survival will also be analyzed as a time-to-event endpoint with the median (Kaplan-Meier estimate) and associated 95% CI (Brookmeyer-Crowley methodology) reported, along with the Kaplan-Meier estimates for PFS rates at 3, 6, 9 and 12 months and associated 95% CIs (log-log transformation methodology of Kalbfleisch-Prentice).

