#### 3.2.2. Secondary Endpoints

Duration of response (DOR)

Duration of response is defined as the time from the first documented response (CR or PR) to the first documented objective progressive disease (PD) or death due to any cause.

Disease control rate (DCR)

Disease control rate is defined as the proportion of patients with objective evidence of CR, PR, or SD, except that there is no requirement for a confirmation of an SD response.

Progression-free survival (PFS)

PFS is defined as the time from the first dosing date to the date of the first documented progression or death due to any cause, whichever occurs first.

Overall survival (OS)

OS is defined as the time between the first dosing date and the date of death.

ORR, DOR, DCR and PFS endpoints will be calculated based on IRC and based on investigator assessment

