Tumor assessments / scans		X		X	X	(X)	Same tumor assessments/scans obtained at screening at the end of every 2 cycles (up to +2 weeks) up to Cycle 4. Thereafter tumor assessments may be performed every 3 cycles (± 7 days), or as clinically indicated, until radiologic PD or initiation of new anticancer therapy (whichever occurs first).  At EOT, tumor assessment must be performed if the prior scan was performed ≥9 weeks prior to discontinuation of treatment if the patient discontinued for reasons other than radiologic disease progression. See also Protocol Section 10.17.  After EOT, patients who discontinued for reasons other than radiologic disease progression should continue to receive tumor assessments every 3 cycles (± 7 days), or as clinically indicated, until radiologic disease progression or initiation of new anticancer therapy (whichever occurs first).

Taiho Oncology, Inc. Statistical Analysis Plan (Phase 2) – Protocol TPU-TAS120-101

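### Phase 2 SAP Table 6 drops progressions found more than 21 days after the last dose from PFS and DOR, a limit the protocol does not set

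*SAP*

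**What the plan says.** **The SAP rule.** Phase 2 SAP 6.4.2, Table 6, note a: an event after the last dose is "counted as a PFS event as long as the PD and/or the death occurs within 21 days since the date of the last dose", provided no other censoring rule (such as new anticancer therapy) applies. Otherwise the patient is censored at the last scan before last dose plus 21 days. Table 6 is titled for PFS, but 6.4.2 names it as the censoring rule for DOR too.

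**The definitions.**
- Protocol 12.2.2.3 runs DOR "to the first documentation of objective tumor progression or death due to any cause, whichever occurs first".
- Protocol 12.2.2.4 runs PFS to the first documented progression or death. On deaths: "Patients who die without a reported disease progression will be considered to have progressed on the date of their death". On missing assessments: "Patients who did not have any on-study assessments and did not die will be censored on the first dosing date". Patients are otherwise censored only if they have no event or start new therapy first.
- Phase 2 SAP 3.2.2 runs PFS "to the date of the first documented progression or death due to any cause, whichever occurs first", and defines DOR likewise.

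None of these refers to time since the last dose.

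**Follow-up after stopping.** In protocol Table 2, "patients who discontinued for reasons other than radiologic disease progression should continue to receive tumor assessments every 3 cycles", until radiologic progression or new therapy. Phase 2 SAP Table 1 repeats this. Protocol 9.17.1 adds: "Every effort should be made to document objective progression even after discontinuation of treatment".

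**The concern.** The SAP contradicts the protocol and its own endpoint section, and discards data that the trial sets out to collect. Protocol 9.17.1 has patients stop treatment for clinical progression without radiologic confirmation, so some who stop early are already worsening. Censoring them three weeks after the last dose is then likely to be informative and can raise late PFS and DOR rates.

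DOR is the key secondary objective. SAP 5.4 times the final analysis so that most responders have at least 6 months of follow-up from response, yet note a ignores progressions found in that period once a responder has been off drug for more than 21 days. None of the sensitivity analyses in SAP 6.4.2.1 lifts the limit: the PFS one changes only who reads the scans. The SAP revision history does not mention the rule.

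**Working it through.** The plan gives no event count or power for PFS or DOR, so there is no stated figure to reproduce. The check compares the rule with the scan schedule and then simulates it.

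**1. Can the next scan fall inside 21 days?** A cycle is 21 days, so scans after Cycle 4 are 3 x 21 = 63 days apart, with a window of 7 days either side.
- If the original calendar continues and stops fall evenly between scans, the share with the next scan inside the limit is 21/63 = 33%. With the window it is 14/63 = 22% to 28/63 = 44%.
- Before Day 84 scans are 2 x 21 = 42 days apart, giving 21/42 = 50% before the +2-week allowance.
- If the 3 cycles run from EOT, the next scheduled scan is 56 to 70 days after EOT, and none falls inside.

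**2. A case needing no assumed rates.** Under the text after protocol Table 8, a patient whose toxicity has not recovered within 21 days of the last dose is discontinued. The EOT visit is 0 to 7 days after that decision (protocol 9.19), so Day 21 to 28 after the last dose. Progression first seen after Day 21, at EOT or later, cannot count. Progression on a scan during the hold still does.

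**3. Simulation of the size.** There were 20,000 patients per scenario. Scans fall at Days 42 and 84 and then every 63 days; progression is dated at the next scan; new therapy before progression censors at the last scan before it. Under the SAP rule, everyone who stops without progression is cut at the last scan by stop + 21 days.

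Assumed, not in the documents: median PFS 6 or 9 months; 10 to 30% stop before radiologic progression; hazard after stopping x1, x2 or x3; 0 to 70% start new therapy a mean of 35 days later; a 24-month cut-off or staggered follow-up of 8 to 26 months. That is 2 x 3 x 3 x 4 = 72 scenarios per follow-up setting. Scans varying in their windows were run with staggered follow-up only.

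Change in percentage points, SAP rule minus protocol rule:

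| Hazard after stopping | 12-month PFS, exact scan days | 12-month PFS, scans varying in windows | 12-month DOR |
|---|---|---|---|
| x1 | -0.9 to 0 | -2.4 to -0.1 | -1.8 to 0 |
| x2 | +0.3 to +5.1 | +0.2 to +3.2 | +0.2 to +4.2 |
| x3 | +0.5 to +6.9 | +0.4 to +5.7 | +0.4 to +6.1 |
| Middle case (20% stop, x2, 50% new therapy) | +1.2 to +1.8 | +0.9 to +1.1 | +1.0 to +1.6 |

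- The PFS extreme is 26.6% against 19.7%, a difference of 6.9 points (median 6, 30% stop, x3, no new therapy, 24 months).
- Events lost (exact days, no deaths): 2 to 29% overall, 8 to 11% in the middle case.
- Median PFS is unchanged in 135 of 144 runs; 7 are higher and 2 lower, each by one 63-day interval. Median DOR is unchanged in 108 of 144.
- If 30% of post-stop events are deaths, the middle case is +0.8 to +1.1 when late deaths count and +1.3 to +1.8 when they are cut too.

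**4. Dependence on the reading.** If row 5 keeps the later scans of patients who never progress while note a removes only late progressions, 12-month PFS rises by +0.1 to +4.1 points even at x1.

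**5. A second model.** It takes medians of 3.2, 6 or 9 months and no new therapy. Patients stop either 0 to 90 days before the progression scan or at a random fraction of their own time to progression. Every scenario moved upward, by about 1 to 9 points at 12 months. Even the random version ties stopping time to progression time, so it is not comparable with x1 above.

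**6. Sampling error.** In 1,500 simulated trials of 100 patients, the 95% half-width of 12-month PFS was 8.8 to 10.5 points.

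**The case against.** **Size.** The documents give none of the rates that drive the bias, its direction depends on how stopping is modelled, and the shifts lie inside sampling error. All of that stands. The trial is single-arm, ORR is the only tested endpoint, and PFS and DOR are descriptive.

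**Extra scans.** The simulation omits the EOT scan, required when the last scan is at least 9 weeks old, and scans done as clinically indicated. Patients stopping for clinical progression may well be scanned promptly. In a similar model, giving every stopper one scan 14 days after stopping (an upper bound on this effect) reduces the middle case from +1.4 to +1.9 points to +1.2 to +1.3. The bias shrinks but remains.

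**Discretion.** Protocol section 12 leaves technical detail to the SAP, and 6.4.2 says its censoring rules follow a 2007 FDA guidance, which cannot be checked here. The rule may have been deliberate. That would not reconcile it with SAP 3.2.2 or the protocol, and the SAP does not declare a departure.

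**Late deaths.** Note a's wording cuts them, but row 2 (death) shows no marker in the Phase 2 text as extracted, while the Phase 1 Expansion table shows one. This is unclear rather than a proven conflict. Row 4 also omits the protocol's condition that the patient did not die, and the table states no precedence among rows. The conflict over progression does not depend on any of this.

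**Row 7 and note d.** This is a separate defect and, on these models, a larger one. It belongs in the repair but not in the size given for the 21-day limit.

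**Conclusion.** The concern holds. On progression, note a conflicts with protocol 12.2.2.3 and 12.2.2.4 and with Phase 2 SAP 3.2.2, and nothing in the plan resolves it. Confidence in the text is high; confidence in the size is low. A higher hazard after stopping is plausible and, under the main reading, is what produces upward bias; with an unchanged hazard that reading gives none. The case for repair rests on the endpoint definitions and the status of DOR, not on the magnitude. It should be settled before PFS and DOR are analysed.

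**What to change.** In the main PFS and DOR analyses:
- Delete the 21-day limit. Count every documented progression or death up to data cut-off unless new anticancer therapy starts first.
- State that row 2 (death) applies whatever the time since last dose and overrides rows 4 and 5, which apply only when no later event occurs.
- Move row 7 and note d to a sensitivity analysis with thresholds matched to the scan schedule. The protocol has no such rule. Its limit of 2 cycles (42 days) in the first 6 months is shorter than the 63-day interval after Cycle 4, so a progression on the on-time Day 147 scan (84 + 63) is censored. Simulated alone, with note a deleted, it removes 14 to 19% of events and adds 6.3 to 7.7 points to 12-month PFS.
- Reconcile row 8 (baseline missing or unreadable), which is also absent from protocol 12.2.2.4, or declare it as a change.

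The 21-day version may stay as a labelled sensitivity analysis. If the sponsor insists on it as the main rule, the minimum is to declare the departure and add PFS and DOR analyses on the protocol definitions. Make the same correction in Table 6 of the Phase 1 Expansion SAP.

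The cost is SAP wording and derivation code; post-EOT scans and survival status are already collected. PFS and DOR estimates may come out slightly less favourable.

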# **6.4.** Efficacy Analyses

#### 6.4.1. Primary Efficacy Analyses

The primary endpoint, Objective Response Rate (ORR), defined as the proportion of patients who achieved best overall response of partial response (PR) or complete response (CR) per RECIST 1.1 based on Independent Review Committee (IRC) in the Efficacy Population, will be summarized by a binomial response rate. ORR will be calculated from the best of overall response recorded from the start of treatment until progression disease or start of subsequent new anticancer treatment. The overall response can be derived based on target lesion response, non-target response as well as the emergence of new lesion for patients with measurable disease at baseline. Table 4 presents the rules to derive the overall response.

The best overall response, CR and PR, will be confirmed with at least 4 weeks intervals of two consecutive time points. A minimum of 6-week interval between initial of treatment (first dose date) and tumor measurement is required for SD. The confirmation rule of the best of overall response is shown in Table 5.

95% confidence interval (binomial proportion confidence interval) for ORR will be constructed with Clopper-Pearson 95% CI. The null hypothesis will be rejected if the 2-sided 95% CI lower

bound is greater than 10%. This translates in observing at least 17 responders out of 100 in the Efficacy Population.

The objective response rate will be created by both independent review and investigator review. The primary endpoints, ORR, assessed with RECIST 1.1, will be displayed in the efficacy tables with both independent and investigator review.

Table 4. Overall Response Assessment with Target/Non-target Lesion and New Lesions

Target Lesions	Non-target Lesions	New Lesions	Overall Response
CR	CR	No	CR
CR	Non-CR/Non-PD or Not all evaluated	No	PR
PR	Non-PD or Not all evaluated	No	PR
SD	Non-PD or Not all evaluated	No	SD
Not all evaluated	Non-PD	No	Not evaluable
PD	Any	Yes or No	PD
Any	PD	Yes or No	PD
Any	Any	Yes	PD

Table 5. Confirmation Rules for Overall Response of PR and CR

Earlier Response	Later Response	Confirmed Response
(to be confirmed)	(confirmation)	
CR	CR	CR
CR	Not CR or missing	SD
PR	CR or PR	PR
PR	SD or PD or missing	SD
PR	SD and then PR (only one SD in between)	PR
SD	n/a – no confirmation needed	SD
PD	n/a – no confirmation needed	PD

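### Phase 2 SAP Table 6 note d treats the planned 63-day gap between the Cycle 4 and Cycle 7 scans as two missed scans, so unless an extra scan falls between them a progression found on time at Cycle 7 is censored at Day 84

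*SAP*

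**What the plan says.** Phase 2 SAP 6.4.2, Table 6, row 7 covers "Death or PD after two or more missed tumor assessments" and takes as its end date the last tumor assessment "before missed assessments". Note d defines the trigger as "having either one of the following two durations being longer than 2 cycles for the first 6 months of treatment, or thereafter 3". No unit is printed after the 3. Two durations are tested and either is enough: between consecutive assessments, or "Duration between the last tumor assessment and death or PD". The Phase 1 Expansion SAP carries the same note.

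Phase 2 SAP Table 1 puts scans "at the end of every 2 cycles (up to +2 weeks) up to Cycle 4", then every 3 cycles with 7 days either side. Protocol 9.17.1 agrees. Cycles are 21 days.

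For DOR, the key secondary objective in Protocol 6.3, the SAP says "The censoring rule is shown in Table 6". The PFS and DOR definitions in Protocol 12.2.2.3 and 12.2.2.4 contain no missed-assessment rule. Neither sensitivity analysis in SAP 6.4.2.1 removes row 7.

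**The concern.** The scan interval widens from 42 to 63 days at Day 84, but note d keeps its 42-day limit until 6 months. Between those two times, a patient who attends every visit meets the definition of having missed two. Row 7 then turns an observed progression into a censoring at the previous scan. Its wording shows that it was meant for patients with real gaps in follow-up, so note d does not implement the row that it serves.

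What is at stake is the reported PFS curve, in particular the 6-month rate that Protocol 12.2.2.4 requires, and DOR. In a single-arm study these are descriptive, but they are the figures that readers will set beside historical results.

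**Working it through.** **Inputs.** Cycle length 21 days (Phase 2 SAP 5.2). Scans due at the end of Cycles 2, 4, 7 and 10: Days 42, 84, 147 and 210. Windows from SAP Table 1: up to +14 days through Cycle 4, ±7 days after. Note d limit: more than 2 × 21 = 42 days. Six months: 182.6 days.

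**Gaps when no scan is missed**

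| Gap | On time | Within windows | Note d |
|---|---|---|---|
| Cycle 2 to 4 | 84 − 42 = 42 | 28 to 56 | flagged above 42 |
| Cycle 4 to 7 | 147 − 84 = 63 | 140 − 98 = 42 to 154 − 84 = 70 | flagged, except at exactly 42 |
| Cycle 7 to 10 | 210 − 147 = 63 | 49 to 77 | depends on the unit of the 3 and on how the 6-month limit is applied |

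Day 147 is 4.8 months, so the Cycle 4 to 7 gap lies inside 6 months whether judged by its start or its end. The Cycle 7 to 10 gap starts inside and ends outside, and note d does not say which counts.

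**Gaps when two scans are missed.** First dose to Cycle 7 is 147 days, Cycle 2 to 10 is 168 and Cycle 4 to 13 is 189. The smallest value between planned visits, using the windows, is 140 days. The 42-day limit is far below this.

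**Deaths.** 84 + 42 = 126, so after an on-time Day 84 scan an on-treatment death on Days 127 to 146 is also flagged, before the next scan is due.

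**Size for PFS.** Assume exponential PFS with true median m months, on-time scans, no extra scans, and every event a scan-detected progression. Then S(t) = 2^(−t/(30.4375 m)). The correct Kaplan-Meier value at 6 months is S(147). Note d removes the drop at Day 147, so the reported value is S(84).

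| m | S(84), reported | S(147), correct | S(84) − S(147) |
|---|---|---|---|
| 3.2 | 0.550 | 0.351 | 0.199 |
| 6 | 0.727 | 0.572 | 0.155 |
| 9 | 0.809 | 0.689 | 0.119 |

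The last column is the share of all patients whose progression is first seen at Cycle 7. With a data cut-off spread evenly over 12 to 24 months (an assumption), about 17% to 21% of observed progressions are censored.

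Median for m = 6: S(210) = 0.451, so the correct median is Day 210, or 6.9 months. With note d, S′(210) = S(84) × S(210)/S(147) = 0.572 and S′(273) = 0.451, so the reported median is Day 273, or 9.0 months. For m = 3.2 it moves from 4.8 to 6.9 months. For m = 9, S(273) = 0.501 and S′(336) = 0.501, so a sample could give 9.0 or 11.0 months without note d and 11.0 or 13.1 with it.

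**With deaths.** Let 30% of events be on-treatment deaths, dated on their day. Deaths on Days 85 to 126 stay events. By simulation, 6-month PFS moves from 0.33 to 0.46, 0.55 to 0.66 and 0.67 to 0.76 for m = 3.2, 6 and 9. For m = 3.2 the median falls from 4.5 to 3.9 months: censoring at Day 84 shrinks the risk set, so the remaining deaths weigh more.

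**Size for DOR.** Assume a true median of 6 months, on-schedule scans, a confirmation scan 28 to 42 days after first response, and first responses at Cycles 2, 4 and 7 in mixes of 80/15/5, 50/40/10 and 30/60/10%. By simulation, 7% to 18% of events are censored and the median moves by about 0 to 0.7 months. One mix is unstable, up to 1.4 months, because its curve sits at 0.5 on a step. The shift also depends on how progression before the confirmation scan is modelled, so it is an order of magnitude only.

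**The case against.** **Extra scans can split the gap.** Protocol 9.17.1 asks for a confirmation scan 4 to 6 weeks after a first response, and clinically indicated scans are allowed. This stands, and the point is conditioned on it. A patient with stable disease at Cycle 4 has no planned scan before Cycle 7.

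**Note a already removes some of these events.** A progression or death after the last dose counts only "as long as the PD and/or the death occurs within 21 days since the date of the last dose of study drug". Progressions found at Cycle 7 in patients off drug for longer are therefore lost in any case, and the 17% to 21% is not all new loss. For deaths the position is unclear: in the Phase 2 table the marker for note a sits on row 1 only, while in the Expansion SAP it is on row 2 as well.

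**Stronger readings that the documents do not support.**
- A reader might infer that the reported 6-month PFS is simply the Day 84 rate. That holds only if nobody dies on Days 85 to 126.
- A reader might infer that every median is inflated. The case of true median 3.2 with 30% deaths shows the opposite.
- A reader might infer that nearly half of all progressions are lost. Figures of 44% to 50% arise only if the 3 means cycles and scan dates are spread evenly over the windows. The unit is not printed and the spread is an assumption. Read as months (about 91 days), the later limit flags no in-window gap, since the longest is 77 days.
- A reader might infer that the efficacy conclusion is compromised. The only decision rule, beginning "The null hypothesis will be rejected if the 2-sided 95% CI lower", concerns ORR and does not use Table 6.

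**Conclusion.** The defect is real and follows from date arithmetic on the SAP's own schedule. With no intermediate scan, a progression at an on-time Cycle 7 scan is censored at Day 84 with no visit missed. In-window late Cycle 4 scans, and some on-treatment deaths before the Cycle 7 scan is due, are caught in the same way.

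In every case tried the 6-month PFS rate is biased upward: by 0.12 to 0.20 if all events are scan-detected progressions, and by about 0.09 to 0.13 if 30% are on-treatment deaths. The median usually rises by about 2 months but can fall. These sizes rest on exponential PFS and perfect attendance; the contradiction itself rests on neither. The DOR shift on the exact schedule looks modest. The note should be fixed, but the primary analysis does not depend on it.

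**What to change.** In both SAPs, replace note d with a visit-based rule. Two or more missed assessments should mean that the allowed windows of two successive scheduled tumor assessments both passed without an adequate assessment, between the last adequate assessment (or first dose if there is none) and the progression or death. Fixed day limits are then not needed.

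The text should also:
- state how cycle delays and out-of-window scans are assigned to visits;
- reconcile the Cycle 2 and 4 scan window, which is up to +2 weeks in SAP Table 1 and Protocol 9.17.1 but ±2 weeks in Protocol section 9, because the rule depends on it;
- say whether note a applies to row 2 in Phase 2;
- apply the same rule to DOR;
- add PFS and DOR sensitivity analyses without row 7, which matches the protocol definitions on this point.

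The cost in each SAP is one footnote, its derivation code (more than a day count, since windows are derived per patient) and two extra outputs. No new data are needed. The reported 6-month PFS rate will probably be less favourable; the direction for the median is less certain.
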